1 PROTOCOL SUMMARY

1.1 SYNOPSIS

Title:	A study to assess Midline Frontal Theta (MFT) power as measured by stimulus-locked electroencephalography (EEG) before and after AKL-T01 treatment for improving attention in pediatric participants ages 8-12 years old with Attention Deficit Hyperactivity Disorder (ADHD)
Hypothesis:	ADHD children receiving 4 weeks of AKL-T01 treatment will show enhancement in MFT activity as measured by stimulus-locked EEG.
Objectives:	
Primary Objective:
 
• Demonstrate enhancement of MFT power measured by stimulus-locked EEG (Perceptual Discrimination Task (PDT)=Stimulus) in children with ADHD following 4 weeks of at-home AKL-T01 treatment. 
Secondary Objective:
 
• Demonstrate normalized MFT power in children with ADHD following 4 weeks of at-home AKL-T01 treatment. 
Exploratory Objectives:
 
• Demonstrate improvement in sustained attention by direct assessment in children with ADHD following 4 weeks of at-home AKL-T01 treatment.• Demonstrate improvement in ADHD symptoms by parent report in children with ADHD following 4 weeks of at-home AKL-T01 treatment.
Endpoints:	
Primary Endpoint:
 
• PDT-locked EEG relative to pre-training 
Secondary Endpoint:
 
• PDT-locked EEG relative to a normative control cohort 
Exploratory Endpoints:
 
• Project EVO Assessment• Test of Variables of Attention (TOVA)• Vanderbilt Assessment
Study Population:	30 children ages 8 to 12 with ADHD from the United States
Description of Study Intervention:	AKL-T01 is a digital therapeutic software for the treatment of attention and inhibitory control deficits in patients with ADHD. AKL-T01 is an investigational medical device known as Software as a Medical Device (SaMD).
Study Duration:	From beginning of enrollment to last subject last visit, 12 months
Participant Duration:	29 Days

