3 OBJECTIVES AND ENDPOINTS

OBJECTIVES	ENDPOINTS
Primary	
Demonstrate enhancement of MFT power measured by stimulus-locked EEG (Perceptual Discrimination Task (PDT)=Stimulus) in children with ADHD following 4 weeks of at-home AKL-T01 treatment.	Change in midline frontal theta power as measured by PDT-locked EEG.
Secondary	
Demonstrate normalized MFT power in children with ADHD following 4 weeks of at-home AKL-T01 treatment.	MFT power of ADHD cohort at Day 28 compared to that of neurotypical cohort at Day 0 (historical controls).
Exploratory	
Demonstrate improvement in attention in children with ADHD following 4 weeks of at-home AKL-T01 treatment.	
Reaction time and reaction time variability as measured by TOVA.Reaction time and reaction time variability as measured by perceptual discrimination task.Reaction time and reaction time variability as measured by ALK-M01 Assessment.

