4 STUDY DESIGN

4.1 OVERALL DESIGN

This study is a single arm, open-label, pilot study to assess midline frontal theta (MFT) power as measured by stimulus-locked electroencephalogram (EEG) before and after treatment with AKL-T01 for improving attention in pediatric participants ages 8-12 years old with attention deficit hyperactivity disorder (ADHD).

All participants enrolled in this study will not be taking ADHD medications, including stimulants, for the duration of the study. Participants who are taking ADHD medications prior to Day 0 must have been stable off of medications for at least 30 days per parent report, or washout of medications at a Screening visit 3 – 7 days prior to Day 0.

At Baseline / Day 0, all eligible participants will complete both resting-state and PDT-locked EEG, as well as the TOVA, Vanderbilt, and AKL-M01 assessments.

All participants will then play AKL-T01 for approximately 25 minutes per day, 5 days per week, for 4 weeks at home.

At Follow-up / Day 28, participants will repeat both resting-state and PDT-locked EEG, as well as the TOVA, Vanderbilt, and AKL-M01 assessments.

All study visits for each participant should be completed during the same time of day (either AM or PM), to maintain consistent data collection and comparison of rater assessment results.

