9 STATISTICAL CONSIDERATIONS

9.1 STATISTICAL HYPOTHESES

OBJECTIVE	HYPOTHESIS
Primary	Children with ADHD, following 4 weeks of digital treatment with AKL-T01, will demonstrate enhancement of MFT power as measured by stimulus-locked EEG.
Secondary	Children with ADHD, following 4 weeks of digital treatment with AKL-T01, will demonstrate normalized MFT power as compared with a neurotypical population.

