9.3 STATISTICAL ANALYSES

All statistical analyses will be conducted using SPSS 22.0 (SPSS Inc.). Group effects for both behavioral and neural measures will be assessed with separate ANOVAs and ANCOVAs with planned follow-up contrasts (Fisher's LSD). The ANCOVA approach is considered to be a more suitable approach when post-test performance that is not conditional / predictable based on pre-test performance is the primary outcome of interest following treatment, as opposed to characterizing gains achieved from pre-training performance (for example, group X session interaction(s)). However, both are appropriate statistical approaches that have been used to assess cognitive training outcomes. Thus, our approach will be to present the p-values for each approach. Planned follow-up contrasts will be used to directly assess changes within each group. To minimize influential data points, we will remove values +/- 2 standard deviations for all group analyses. For correlations tested, we will use a more stringent outlier removal procedure (Cook's D> 1) given the smaller cohort size and possible inflated change scores.

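### Section 9.3 deletes values beyond 2 SD before ordinary tests, without naming what is screened or planning an all-values analysis: single-pass type I error for the primary contrast is about 5% to 10%, depending on the reading

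*Combined protocol and SAP*

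**What the plan says.** Section 9.3 sets the rule: "To minimize influential data points, we will remove values +/- 2 standard deviations for all group analyses". The tests it names are separate ANOVAs and ANCOVAs with Fisher's LSD follow-up contrasts, and of these contrasts it says: "Planned follow-up contrasts will be used to directly assess changes within each group". A different rule, Cook's D above 1, applies only to correlations and is justified as "given the smaller cohort size and possible inflated change scores".

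The primary endpoint in section 3 is "Change in midline frontal theta power as measured by PDT-locked EEG". The secondary endpoint in the same table compares single-visit values: the ADHD cohort at Day 28 against historical neurotypical children at Day 0. The primary hypothesis in section 9.1 is directional: children "will demonstrate enhancement of MFT power as measured by stimulus-locked EEG". Section 4.1 states "This study is a single arm, open-label, pilot study", and the synopsis plans "30 children ages 8 to 12 with ADHD from the United States".

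Neither section 9 nor any other part of the document gives:
- the variable screened (visit value, change score or residual);
- the group or visit that supplies the mean and SD;
- the number of passes;
- the handling of the paired value when one visit is removed;
- an adjusted standard error;
- an analysis that keeps all values;
- a significance level.

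**The concern.** In clean normal data about 4.6% of values lie beyond 2 SD. Deleting them shrinks the sample SD, and an ordinary t or F test then treats the smaller SD as real precision. Intervals become too narrow and p-values too small.

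There is no concurrent control, so the primary claim rests on the pre/post contrast within one group of at most 30 children. If the error rate of that contrast depends on a choice the plan leaves open, the choice can be made after the data are seen. A reader would also have no all-values result against which to judge the published p-value.

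**Working it through.** The plan states no alpha, power or effect size, so it has no figure of its own to reproduce. The check asks what the stated rule does to the test that follows it.

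**Inputs.**
- From the document: 30 ADHD children (synopsis); 24 neurotypical children in the feasibility study (section 2.1); primary endpoint a change (section 3); 2 SD rule and ordinary tests (section 9.3).
- Assumed: two-sided 5%; normal data; true change zero; one pass; contrast equal to a paired t-test; child dropped from the pair if either visit value is removed; pre/post correlation 0.5, 0.7 or 0.9. Sample sizes of 20 to 30 allow for attrition and the compliance rule in section 9.2.

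**Step 1: large-sample mechanism, change scores screened.**
- Fraction kept: P = 2Φ(2) − 1 = 0.9545.
- With g = 4φ(2) = 4 × 0.0540 = 0.216, variance of kept values = 1 − g/P = 1 − 0.216/0.9545 = 0.774. SD ratio = √0.774 = 0.88.
- Variance the ordinary test reports for the mean, in units of σ²/n: 0.774/0.9545 = 0.811.
- Actual variance of the screened mean, allowing for limits centred on the sample mean: [(P − g)(1 + 2g) + g²]/P² = [0.7385 × 1.432 + 0.0466]/0.911 = 1.21.
- Reported over true standard error: √(0.811/1.21) = 0.82. The nominal 1.96 therefore acts as 1.96 × 0.82 ≈ 1.60, a two-sided error of about 11%.

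**Step 2: simulation at the trial's size** (200,000 replicates per cell; main cells independently reproduced). Three rates in a cell are for correlation 0.5 / 0.7 / 0.9.

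| What is screened | Type I error, n = 20-30 | Favourable direction only, n = 30 (nominal 2.5%) | Mean children lost, n = 30 | Trials losing at least one |
|---|---|---|---|---|
| Nothing | 5.0% | 2.5% | 0 | 0% |
| Change scores | 10.0-10.3% | 5.2% | 1.2 | 82% |
| Each visit, within ADHD | 7.2-7.4% / 6.3-6.5% / 5.6% | 2.8-3.8% | 1.7-2.2 | 93-97% |
| Each visit, ADHD plus 24 neurotypical (equal means) | 6.0-6.4% / 5.6-5.9% / 5.3-5.4% | – | – | – |
| Both visits, one common mean and SD | 4.9-5.0% | 2.5-2.6% | 1.8-2.4 | 95-98% |

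The children lost in this table have no artefact. With change-score screening at n = 30, the SD falls to 0.89 of its unscreened value and the nominal 95% interval covers 90%.

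**Step 3: the reading that keeps the level.** With both visits pooled and a true shift of 0.5 SD of change at n = 30, the estimated shift falls to 0.44-0.48 SD, and power falls from 75% to 67-71%. When there is a real increase, the common limits preferentially remove low pre-treatment and high post-treatment values.

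**Step 4: other models and distributions.**
- Within-ADHD contrast with an error term pooled over 30 ADHD and 24 neurotypical children, change scores: 10.1% screened within group, 7.8% screened across groups.
- ANCOVA group effect, screened within group: 6.7% to 9.8%.
- Secondary comparison, 30 against 24: 10.1% screened per group, 5.0% pooled.
- Heavy-tailed change scores (t with 5 and 3 df), change-score screening: 8.9% and 8.3%.
- Skewed visit values (log-normal, log-SD 0.8), n = 30: 4.0-4.1% with all values, 7.4-7.7% change scores, 5.4-7.6% separate visits, 4.6-4.9% pooled.
- Repeated screening of change scores, which the text does not rule out, n = 30: about 17.7%.

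**The case against.** The strongest reply is that 10% belongs to the less natural reading. Section 9.3 applies the rule to values, uses change scores as a separate term when explaining the correlation rule, and describes models in pre-test, post-test and session scores. Visit-value screening then gives 4.9-7.4%, and at correlations of 0.7 to 0.9 the excess is small. This stands: visit values are at least as well supported a reading. Change scores are not excluded, however, because the primary endpoint is itself a change.

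Second, the doubling needs clean normal change scores, which is where an outlier rule is least needed. Skewed, heavy-tailed or contaminated data gave 7.4-8.9% for change-score screening. This also stands, so 10% is the upper end for one pass on change scores. The inflation shrinks but does not disappear.

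Third, no stated error rate is breached, the study is a pilot, and the rule is symmetric and written in advance. Change-score and separate-visit screening leave the estimate unbiased. All true, but the objective is to demonstrate enhancement and p-values will be reported. A rule with its variable, reference group and pair handling left open is only partly written in advance.

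Fourth, EEG data can contain gross artefacts, and a plain all-values t-test then loses much power. That is correct and has shaped the remedy.

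**Conclusion.** The concern holds. Two facts do not depend on any assumption: the rule is not defined well enough to be applied in only one way, and no all-values analysis is planned. The numerical harm depends on the reading. Under a two-sided 5% level, normal data, zero change and one pass, three of the four readings make the primary p-value too small, from slightly (5.3%) to about twofold (10.3%). The fourth keeps the level but attenuates a true effect by roughly 4% to 12% (0.48/0.50 to 0.44/0.50) and costs power. All four discard valid children by design. The flaw can be corrected in the analysis plan and should be fixed before analysis.

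**What to change.** 1. For the primary and secondary objectives, make the analysis of all technically valid EEG values primary. Exclude a recording only for artefact or recording failure, judged without knowledge of visit. State the significance level.
2. Keep any 2 SD exclusion as a sensitivity analysis, with the screened variable, reference group, single pass and handling of the paired value fixed in advance.
3. Pre-specify a trimmed-mean (Yuen) test with 10% per tail as the robust companion, or as the primary test if gross artefacts are expected to survive quality control. Its simulated type I error is 5.1-5.3% at n = 20-30 with normal data.

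**Cost.** No participants or visits are added. The artefact review without knowledge of visit is a procedural step that the protocol does not now describe. Intervals are 9-10% wider than with change-score screening at n = 20-30. On clean normal data at n = 30 with a true shift of 0.5 SD, power is 75% with all values against 78% screened on change scores. The screened figure falls to 66% once its level is brought back to 5%.

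The real cost arises if artefacts pass review. The document gives no artefact rate, so these cases are assumptions:

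| Assumed contamination (six-fold SD) | All values | Screened | 10% trimmed mean |
|---|---|---|---|
| 5% of change scores | 51% | 72% (type I error 7.5%) | 66% (type I error 5.1%) |
| 2.5% of visit values, correlation 0.5-0.9 | 36-51% | 65-71% by visit, 64-66% pooled | 65-67% (type I error 5.0-5.1%) |

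The trimmed mean recovers most of the lost power at the correct level. It should therefore be a planned analysis alongside the artefact review and not be left optional.

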10 SUPPORTING DOCUMENTATION AND OPERATIONAL CONSIDERATIONS

10.1 CONFIDENTIALITY AND PRIVACY

Participant confidentiality and privacy is strictly held in trust by the participating investigators, their staff, and the sponsor(s) and their interventions. The study protocol, documentation, data, and all other information generated will be held in strict confidence. No information concerning the study or the data will be released to any unauthorized third party without prior written approval of the sponsor.

10.2 DATA HANDLING AND RECORD KEEPING

10.2.1 DATA COLLECTION AND MANAGEMENT RESPONSIBILITIES

Data collection is the responsibility of the clinical trial staff at the site under the supervision of the principal investigator. The investigator is responsible for ensuring the accuracy, completeness, legibility, and timeliness of the data reported.

All source documents should be completed in a neat, legible manner to ensure accurate interpretation of data. Data recorded in the electronic case report form (eCRF) derived from source documents should be consistent with the data recorded on the source documents.

10.2.2 STUDY RECORDS RETENTION

Study documents should be retained for a minimum of 2 years after the last approval of a marketing application in an International Conference on Harmonization (ICH) region and until there are no pending or contemplated marketing applications in an ICH region or until at least 2 years have elapsed since the formal discontinuation of clinical development of the study intervention. These documents should be retained for a longer period, however, if required by local regulations. No records will be destroyed without the written consent of the sponsor. It is the responsibility of the sponsor to inform the investigator when these documents no longer need to be retained.

10.3 PROTOCOL DEVIATIONS

A protocol deviation is any noncompliance with the clinical trial protocol, ICH GCP, or Manual of Procedures (MOP) requirements. The noncompliance may be either on the part of the participant, the investigator, or the study site staff. As a result of deviations, corrective actions are to be developed by the site and implemented promptly.

